## 8.2.19 EQ-5D-5L

The subject will select which best describes his own health state at the study visit in the following 5 dimensions: Mobility, Self-care, Usual Activities, Pain / discomfort, and Anxiety / depression. The subject will also select a point on a scale drawn like a thermometer to indicate how good or bad the health state is, with best state as '100' and worst state as '0'.

A unique health state is defined by combining 1 level from each of the 5 dimensions. A total of 3125 possible health states is defined in this way. Each state is referred to in terms of a 5 digit code. For example, state 11111 indicates no problems on any of the 5 dimensions, while state 12345 indicates no problems with mobility, slight problems with washing or dressing, moderate problems with doing usual activities, severe pain or discomfort and extreme anxiety or depression. EQ-5D-5L health states will be converted into a single index value. This index value will be derived using the EQ-5D-5L\_Crosswalk\_Index\_Value\_Calculator.v2.xls [[van Reenen, 2015](#)].

Index values are defined for several countries. Not all countries participating in this study are available in the Index Value Calculator. For this, the United Kingdom value set is used for all subjects, regardless whether their country is available in the calculator.

If one or more of the 5 dimensions are missing, the index value cannot be derived and is missing as well.

**Figure 4: EQ-5D-5L**

Under Each heading, please tick ONE box that best describes your health TODAY.

**Mobility**

- I have no problems in walking about
- I have slight problems in walking about
- I have moderate problems in walking about
- I have severe problems in walking about
- I am unable to walk about

**Self-Care**

- I have no problems washing or dressing myself
- I have slight problems washing or dressing myself
- I have moderate problems washing or dressing myself
- I have severe problems washing or dressing myself
- I am unable to wash or dress myself

**Usual Activities (eg, work, study, housework, family or leisure activities)**

- I have no problems doing my usual activities
- I have slight problems doing my usual activities
- I have moderate problems doing my usual activities
- I have severe problems doing my usual activities
- I am unable to do my usual activities

**Pain/Discomfort**

- I have no pain or discomfort
- I have slight pain or discomfort
- I have moderate pain or discomfort
- I have severe pain or discomfort
- I have extreme pain or discomfort

[figure not shown]
**Anxiety/Depression**

- I am not anxious or depressed
- I am slightly anxious or depressed
- I am moderately anxious or depressed
- I am severely anxious or depressed
- I am extremely anxious or depressed

**Figure 5: EQ-5D-5L (VAS)**

To help people say how good or bad a health state is, we have drawn a scale (rather like a thermometer) on which the best state you can imagine is marked 100 and the worst state you can imagine is marked 0.

We would like you to indicate on this scale how good or bad your own health is today, in your opinion. Please do this by drawing a line from the box below to whichever point on the scale indicates how good or bad your health state is today.

## 8.2.20 WPAI-GH

The subject will answer questions about the effect of his / her health on the ability to work or perform regular activities. General health is defined as any symptoms relating to physical or emotional well-being.

WPAI outcomes are expressed as impairment percentages, with higher numbers indicating greater impairment and less productivity, ie, worse outcomes, as follows:

Questions:

Q1 = currently employed

Q2 = hours missed due to health problems

Q3 = hours missed other reasons

Q4 = hours actually worked

Q5 = degree health affected productivity while working

Q6 = degree health affected regular activities

Scores:

- Percent **work time missed due to health**\*:  $Q2/(Q2+Q4) \times 100$
- Percent **impairment while working due to health**\*:  $Q5/10 \times 100$
- Percent **overall work impairment due to health**\*:  
$$(Q2/(Q2+Q4)+[(1-(Q2/(Q2+Q4)))\times(Q5/10)]) \times 100$$
- Percent **activity impairment due to health**:  $Q6/10 \times 100$

If any of the contributing questions for a score is missing, the score cannot be calculated.

\* Irrespective of any answers given for Q2 to Q5 these scores will be calculated only if Q1 is answered “YES”.

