## 8 Data Handling Conventions

### 8.1 Missing Data

#### 8.1.1 Imputation of Non-Date Missing Data

Per the protocol, subjects will be encouraged to remain in the study for the remainder of the phase during which they discontinue IMP, in order to collect further study assessments. Missing efficacy data will occur if a subject withdraws consent for additional post-discontinuation assessments. Below is how the missing efficacy data are handled in the key efficacy analyses:

- The primary endpoint analysis considers subjects discontinuing from the study before Week 25 as Non-responders, except for subject who discontinue due to the Ukraine war (see Section 10.2). This consideration is modified in the sensitivity analyses detailed in Section 10.2.1.
- The three continuous key secondary efficacy endpoints are analyzed with MMRM under the Missing at Random (MAR) assumption. No missing data imputation is required for this analysis approach.
- Tipping point analyses will be performed for the key secondary endpoint analyses.

The handling of missing data from questionnaires, CSMs, and other data collection instruments is described in the respective section of the specific instrument.

Subjects with the designation of relationship to IMP and/ or oral corticosteroid treatment for adverse events (AEs) and serious adverse events (SAEs) missing will have the worst case assumed to impute the relationship to IMP:

Relationship as entered in eCRF		Imputed relationship *	
to IMP	to oral corticosteroid treatment	to IMP	to oral corticosteroid treatment
missing	missing	related	not related
related	missing	related	not related
not related	missing	not related	related **
missing	related	not related	related
missing	not related	related	not related

\* Italic font is used for imputed values

\*\* Only if start of oral corticosteroid treatment was before or at start of AE, otherwise *not related*

There will be no other imputation for missing data other than as described in Section 8.1.2 for partial dates and times.

If the study is terminated early, all available data will be listed, and a review carried out by the study team to assess which statistical analyses are to be performed.

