**Figure 6: WPAI-GH**

The following questions ask about the effect of your health problems on your ability to work and perform regular activities. By health problems we mean any physical or emotional problem or symptom. *Please fill in the blanks or circle a number, as indicated.*

1. Are you currently employed (working for pay)?  NO  YES

*If NO, check "NO" and skip to question 6.*

The next questions are about the **past 7 days**, not including today.

2. During the past seven days, how many hours did you miss from work because of your health problems? *Include hours you missed on sick days, times you went in late, left early, etc., because of your health problems. Do not include time you missed to participate in this study.*

HOURS

3. During the past seven days, how many hours did you miss from work because of any other reason, such as vacation, holidays, time off to participate in this study?

HOURS

[figure not shown]
4. During the past seven days, how many hours did you actually work?

HOURS *(If "0", skip to question 6.)*

5. During the past seven days, how much did your health problems affect your productivity while you were working?

*Think about days you were limited in the amount or kind of work you could do, days you accomplished less than you would like, or days you could not do your work as carefully as usual. If health problems affected your work only a little, choose a low number. Choose a high number if health problems affected your work a great deal.*

Consider only how much health problems affected productivity while you were working.

[figure not shown]

CIRCLE A NUMBER

6. During the past seven days, how much did your health problems affect your ability to do your regular daily activities, other than work at a job?

*By regular activities, we mean the usual activities you do, such as work around the house, shopping, childcare, exercising, studying, etc. Think about times you were limited in the amount or kind of activities you could do and times you accomplished less than you would like. If health problems affected your activities only a little, choose a low number. Choose a high number if health problems affected your activities a great deal.*

Consider only how much health problems affected your ability to do your regular daily activities, other than work at a job.

CIRCLE A NUMBER

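### Read literally, the WPAI missing-item rule discards an overall work impairment score that the SAP's own formula fixes at 100% when an employed subject worked no hours and lost some to health

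*SAP*

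**What the plan says.** SAP 8.2.20 derives four WPAI-GH percentages. Three are work scores, calculated only for subjects who report being employed (Q1 = YES). The fourth, activity impairment, uses Q6 alone. Scores run "with higher numbers indicating greater impairment and less productivity, ie, worse outcomes". Overall work impairment combines Q2, Q4 and Q5, where "Q4 = hours actually worked" and "Q5 = degree health affected productivity while working". The section has one missing-data rule: "If any of the contributing questions for a score is missing, the score cannot be calculated".

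The questionnaire itself (SAP Figure 6 and Protocol Appendix 13) carries an instruction at question 4 on hours worked: "If '0', skip to question 6". A subject who worked no hours is therefore never asked Q5.

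No other section changes this. SAP 8.1.1 states: "The handling of missing data from questionnaires, CSMs, and other data collection instruments is described in the respective section of the specific instrument". It then rules out any further imputation apart from partial dates and times. Apart from the Q1 condition, SAP 8.2.20 has no special case, and none for Q4 = 0. SAP 8.2.6 sets a change to missing if either the reference or the visit value is missing. SAP 10.6 and Table 12 list overall work impairment as an exploratory continuous variable, summarised descriptively with no comparison between sequences.

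**The concern.** A blank Q5 can mean two things: the subject failed to answer, or the form told the subject not to answer. The rule in SAP 8.2.20 does not separate them. In the second case, with health-related hours missed, the blank carries no missing information, because Q5 has weight zero in the formula.

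The loss is also selective. It is triggered by having worked no hours, and every score lost this way is 100%. An employed subject off work all week for health would appear at 100% in the table of work time missed and be absent from the table of overall work impairment at the same visit. What is at stake is the accuracy of the by-visit means of this one score, and the completeness of its changes from Baseline and from Week 25.

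**Working it through.** **Inputs.** The formula and the missing-item rule come from SAP 8.2.20, the skip from SAP Figure 6 and Protocol Appendix 13, and the rule for change from SAP 8.2.6. The plan states no numerical result to reproduce.

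**Formula.** Let a = Q2 / (Q2 + Q4). Work time missed = 100 × a. Overall work impairment = 100 × [a + (1 − a) × Q5/10].

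**No hours worked, some lost to health (Q2 > 0, Q4 = 0).** With Q2 = 40: a = 40/40 = 1, the weight on Q5 is 1 − 1 = 0, and the score is 100 × [1 + 0 × Q5/10] = 100%. Evaluating every Q5 from 0 to 10 gives 100% each time. Q2 = 8 gives the same result. The written rule returns missing.

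**Nearly no hours worked, for contrast.** With Q2 = 36 and Q4 = 4: a = 0.9, and the score runs from 90% (Q5 = 0) to 100% (Q5 = 10). With Q2 = 39 and Q4 = 1 it runs from 97.5% to 100%. These subjects are asked Q5 and are kept. The skip removes only subjects with Q4 = 0.

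**No hours worked, none lost to health (Q2 = Q4 = 0).** The ratio is 0/0. Work time missed and overall work impairment are undefined, and missing is correct.

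**Effect on a visit mean.** Suppose k of n employed subjects have Q2 > 0 and Q4 = 0, and the rest average m. The rule reports m. Scoring everyone gives [100k + (n − k)m]/n, so the shortfall is k(100 − m)/n. The documents give none of k, n or m. With n = 20 and m = 40% assumed:

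| k of 20 | Mean under the rule | Mean with all scored | Shortfall |
|---|---|---|---|
| 1 | 40% | (100 + 19 × 40)/20 = 43% | 3 points |
| 2 | 40% | (200 + 18 × 40)/20 = 46% | 6 points |
| 4 | 40% | (400 + 16 × 40)/20 = 52% | 12 points |
| 6 | 40% | (600 + 14 × 40)/20 = 58% | 18 points |

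**Effect on change.** A subject at 100% at Baseline and 30% at Week 25 should contribute 30 − 100 = −70 points. A subject at 30% at Baseline and 100% at Week 25 should contribute 100 − 30 = +70 points. Under the rule neither contributes. Lost improvements and lost deteriorations pull the mean change in opposite directions, so its net bias has no sign that can be derived from the documents.

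**The case against.** The strongest reply is that SAP 8.2.20 need not be read literally. It speaks of contributing questions that are missing. An item skipped by design is arguably not missing, and an item with weight zero arguably does not contribute. SAP 8.2 also says that its derivations are general descriptions and that separate dataset specifications, which are not available here, hold the full detail. The correct handling may be written there. This stands as a caution about what will actually be programmed. It does not cure the text: Q5 is a term in the formula, SAP 8.1.1 points back to 8.2.20 as the place for the rule, and 8.2.20 makes no exception for the skip. Other instrument sections do make such provisions: SAP 8.2.18 deals with not-applicable answers, and SAP 8.2.21 tolerates one missing item per scale.

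A second reply is that little is lost. Work time missed is still 100% for these subjects, activity impairment is still scored from Q6, and impairment while working is rightly not calculable without Q5. Return to work therefore remains visible in work time missed. That also stands.

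Two stronger readings are tempting. A reader might infer that the most impaired subjects drop out of the WPAI analysis. They do not: one of four scores is affected. Nor are all affected subjects severely impaired, because the formula ignores Q3 (hours missed for other reasons). A reader might also infer that benefit on IgPro20 is understated. The documents do not support that: subjects who worsen to fully off work are lost as well, and SAP 10.6 plans no between-sequence comparison of this score.

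**Conclusion.** The point holds as a defect in one written rule. For employed subjects with Q2 > 0 and Q4 = 0, the SAP's formula determines overall work impairment as 100%, and the SAP's missing-item rule, read literally, discards it. The visit mean is biased downward whenever such subjects exist and the others average below 100%. The size is k(100 − m)/n. The 3 to 18 points shown rest on assumed values and illustrate the arithmetic; they do not estimate impact. Changes are lost in both directions, and their net bias cannot be signed.

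The consequence is small. This is a single exploratory, descriptive score. No hypothesis test, multiplicity step, primary result or key secondary result depends on it. The conclusion assumes that the dataset specifications follow the SAP text as written.

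**What to change.** Add to SAP 8.2.20:

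- If Q1 = YES, Q2 > 0 and Q4 = 0, percent overall work impairment is 100. This imputes nothing; it is the value the formula already gives.
- If Q2 = Q4 = 0, work time missed and overall work impairment stay missing, because the ratio is undefined.
- Impairment while working stays missing whenever Q5 is skipped.

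The cost is a few lines of SAP text and one condition in the derivation code. There is one small downside. Because Q3 is outside the formula, a subject with Q2 = 2, Q3 = 38 and Q4 = 0 also scores 100%, since 2/(2 + 0) = 1, although only two hours were lost to health. The existing derivation of work time missed already does the same. Flagging such cases in the listing is enough.

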**Figure 6: WPAI-GH**

The following questions ask about the effect of your health problems on your ability to work and perform regular activities. By health problems we mean any physical or emotional problem or symptom. *Please fill in the blanks or circle a number, as indicated.*

1. Are you currently employed (working for pay)?  NO  YES

*If NO, check "NO" and skip to question 6.*

The next questions are about the **past 7 days**, not including today.

2. During the past seven days, how many hours did you miss from work because of your health problems? *Include hours you missed on sick days, times you went in late, left early, etc., because of your health problems. Do not include time you missed to participate in this study.*

HOURS

3. During the past seven days, how many hours did you miss from work because of any other reason, such as vacation, holidays, time off to participate in this study?

HOURS

[figure not shown]
4. During the past seven days, how many hours did you actually work?

HOURS *(If "0", skip to question 6.)*

5. During the past seven days, how much did your health problems affect your productivity while you were working?

*Think about days you were limited in the amount or kind of work you could do, days you accomplished less than you would like, or days you could not do your work as carefully as usual. If health problems affected your work only a little, choose a low number. Choose a high number if health problems affected your work a great deal.*

Consider only how much health problems affected productivity while you were working.

[figure not shown]

CIRCLE A NUMBER

6. During the past seven days, how much did your health problems affect your ability to do your regular daily activities, other than work at a job?

*By regular activities, we mean the usual activities you do, such as work around the house, shopping, childcare, exercising, studying, etc. Think about times you were limited in the amount or kind of activities you could do and times you accomplished less than you would like. If health problems affected your activities only a little, choose a low number. Choose a high number if health problems affected your activities a great deal.*

Consider only how much health problems affected your ability to do your regular daily activities, other than work at a job.

CIRCLE A NUMBER

## 8.2.21 TSQM-9

The TSQM-9 is a 9-item general instrument that measures the major dimensions of satisfaction with a medication. Scores on the TSQM-9 range from 0 (indicating poor satisfaction) to 100 (indicating perfect satisfaction). Scores on the Effectiveness (3 items), Convenience (3 items), and Global Satisfaction (3 items) scales will be assessed in a cross-sectional manner. If more than one item score is missing, the scale score should not be calculated, and set to missing.

### Effectiveness

Effectiveness scale score =  $[(\text{Item 1} + \text{Item 2} + \text{Item 3} - 3) / 18] \times 100$

If one item is missing:

Effectiveness scale score =  $[(\text{Item 1?} + \text{Item 2?} + \text{Item 3?} - 2) / 12] \times 100$

### Convenience

Convenience scale score =  $[(\text{Item 4} + \text{Item 5} + \text{Item 6} - 3) / 18] \times 100$

If one item is missing:

Convenience scale score =  $[(\text{Item 4?} + \text{Item 5?} + \text{Item 6?} - 2) / 12] \times 100$

### Global satisfaction

First recode Item 9: Item 9\_R =  $(\text{Item 9} - 1) \times 4/6 + 1$

Overall satisfaction scale score =  $[(\text{Item 7} + \text{Item 8} + \text{Item 9_R} - 3) / 12] \times 100$

If one item is missing:

Overall satisfaction scale score =  $[(\text{Item 7?} + \text{Item 8?} + \text{Item 9_R?} - 2) / 8] \times 100$

**Figure 7: TSQM-9**

1. How satisfied or dissatisfied are you with the ability of the medication to prevent or treat your condition?	 Extremely Dissatisfied  Very Dissatisfied  Dissatisfied  Somewhat Satisfied  Satisfied  Very Satisfied  Extremely Satisfied	5. How easy or difficult is it to plan when you will use the medication each time?	 Extremely Difficult  Very Difficult  Difficult  Somewhat Easy  Easy  Very Easy  Extremely Easy
2. How satisfied or dissatisfied are you with the way the medication relieves your symptoms?	 Extremely Dissatisfied  Very Dissatisfied  Dissatisfied  Somewhat Satisfied  Satisfied  Very Satisfied  Extremely Satisfied	6. How convenient or inconvenient is it to take the medication as instructed?	 Extremely Inconvenient  Very Inconvenient  Inconvenient  Somewhat Convenient  Convenient  Very Convenient  Extremely Convenient
3. How satisfied or dissatisfied are you with the amount of time it takes the medication to start working?	 Extremely Dissatisfied  Very Dissatisfied  Dissatisfied  Somewhat Satisfied  Satisfied  Very Satisfied  Extremely Satisfied	7. Overall, how confident are you that taking this medication is a good thing for you?	 Not at All Confident  A Little Confident  Somewhat Confident  Very Confident  Extremely Confident
4. How easy or difficult is it to use the medication in its current form?	 Extremely Difficult  Very Difficult  Difficult  Somewhat Easy  Easy  Very Easy  Extremely Easy	8. How certain are you that the good things about your medication outweigh the bad things?	 Not at All Certain  A Little Certain  Somewhat Certain  Very Certain  Extremely Certain
		9. Taking all things into account, how satisfied or dissatisfied are you with this medication?	 Extremely Dissatisfied  Very Dissatisfied  Dissatisfied  Somewhat Satisfied  Satisfied  Very Satisfied  Extremely Satisfied

## 8.2.22 CDASI

The Evaluating Physician will assess 4 disease areas (Extent [anatomical locations], Gottron's Hands, Periungual, and Alopecia) for activity and damage and provide a total score for each (see [Figure 8](#)). The total CDASI score is the sum of the total activity score and the total damage score.

Range of total activity score: 0 – 100

Range of total damage score: 0 – 32

Range of total CDASI score: 0 – 132

Figure 8: CDASI

**Cutaneous Dermatomyositis Disease Area and Severity Index (CDASI) ver02**  
Select the score in each anatomical location that describes the most severely affected dermatomyositis-associated skin lesion

E x t e n t	Anatomical Location	activity			damage	
		Erythema	Scale	Erosion/ Ulceration	Poikiloderma (Dyspigmentation or Telangiectasia)	Calcinosis
	0-absent 1-pink; faint erythema 2-red 3-dark red	0-absent 1-scale 2-crust; lichenification	0-absent 1-present	0-absent 1-present	0-absent 1-present	
Scalp						Scalp
Malar Area						Malar Area
Periorbital						Periorbital
Rest of the face						Rest of the face
V-area neck (frontal)						V-area neck (frontal)
Posterior Neck						Posterior Neck
Upper Back & Shoulders						Upper Back & Shoulders
Rest of Back & Buttocks						Rest of Back & Buttocks
Abdomen						Abdomen
Lateral Upper Thigh						Lateral Upper Thigh
Rest of Leg & Feet						Rest of Leg & Feet
Arm						Arm
Mechanic's Hand						Mechanic's Hand
Dorsum of Hands (not over joints)						Dorsum of Hands (not over joints)
Gottron's – Not on Hands						Gottron's – Not on Hands

**Gottron's – Hands**  
Examine patient's hands and double score if papules are present

0-absent 1-pink; faint erythema 2-red erythema 3-dark red	Ulceration	Examine patient's hands and score if damage is present
		0-absent 1-dyspigmentation 2-scarring

**Periungual**  
Periungual changes (examine)

0-absent 1-pink/red erythema/microscopic telangiectasias 2-visible telangiectasias		
--	--	--

